## 7 CLINICAL DATABASE PROCESSING

### 7.1 General information

The clinical database is processed and generated according to The Clinical Data Interchange Standards Consortium (CDISC). CDISC is a Standard Developing Organization which develops and publishes standards to normalise the structure of clinical study data and thereby simplify submissions to and reviews by authorities such as the Food and Drug Administration (FDA).

The CDISC standards for clinical studies are the Study Data Tabulation Model (SDTM) and the Analysis Data Model (ADaM). The study data will be structured into a database model reflecting the SDTM and be compliant to SDTM Implementation Guide (SDTM-IG) version 3.2. The data used for statistical analysis will be structured to reflect the Analysis Data Model (ADaM) and be compliant to ADaM Implementation Guide (ADaM-IG) version 1.1.

Data values are collected according to, or mapped into, Controlled Terminology (CT) codelists defined by CDISC, whenever possible. The codelists are updated biannually at CTC and the latest version available at study start will be used. As per default, CT codelists will be used in all tables, listings, and figures. Custom codelists for test or parameter names will be used if applicable upon Sponsor's request, to align with protocol texts, or to adhere to other standard naming conventions (e.g., PK parameter name "Tmax" will be used instead of the CDISC term "Time of CMAX"). These custom codelists will be mapped in the "Parameter Name" field in the ADaM structure, while the CT will be kept in the SDTM predecessor fields to provide traceability back to CDISC codelists.

#### 7.1.1 CDISC Compliance

Full CDISC compliance will not be claimed for this study. The clinical database will be processed and generated according to CDISC standard to the greatest possible extent, but full compliance will not be claimed. No CDISC documentation (e.g., Define XML, Annotated eCRF, SDTM Reviewer's Guide and ADaM Reviewer's Guide) will be generated.

### 7.2 Database modeling of study design

The study design is mapped to a SDTM study design model containing the following structural components:

**EPOCH:** An interval of time in the planned conduct of a study. An epoch is associated with a purpose (e.g., screening, randomization, treatment, follow-up), and applies across all arms of the study. Study epochs follow a controlled terminology to represent the different study parts (e.g. SCREENING, TREATMENT, FOLLOW-UP)

[figure not shown]
**ELEMENT:** Building blocks used to build up the entire study length for all subjects. Information on ELEMENTs is extracted from the study design and schedule of events in the protocol. ELEMENTs are defined to span the entire study without gaps. One EPOCH may contain one or several ELEMENTs. All ELEMENTs must have transition rules in accordance with the protocol to determine start and end.

**ARM:** Subjects are allocated to study arms depending on the study design, either by randomization or other allocation processes defined in the study protocol. ARMs are defined as the total number of planned ways a subject can go through the study (unique combination of study ELEMENTs). All ARMs must contain a unique sequence of ELEMENTs.

**VISIT:** Study visits are defined as planned timepoints during the study where study data is collected. A visit can be performed in clinic, by off-site contact with study personnel (phone call, video conference or similar), or by subject initiated recordings of data. The visit schedule is extracted from protocol and eCRF design.

A schematic representation of the SDTM study design is presented in Figure 1.

**Figure 1 Schematic representation of the SDTM study design**

\* End of study is modeled as a unique visit, but is performed together with the last participation in the study.

## 8 STATISTICAL DELIVERABLES

The following items will be delivered:

- Statistical analyses, summary tables, listings and figures as described in Section 10.
- Clinical study database delivered as a SAS-export file.

## 9 STATISTICAL METHODOLOGY

Generally, all collected data will be listed. Listings will be sorted by treatment followed by patient.

Due to small sample size, there will be no summaries using site as a grouping variable. However, site will be specified in listings.

Details on statistical analyses and descriptive summaries are specified below. A complete definition of output produced is given in Section 10 below.

All statistical analysis and descriptive summaries will be performed using SAS version 9.4 or later (SAS institute, Cary, NC).

### 9.1 Analysis of the primary endpoints

#### 9.1.1 *Adverse events*

An overview of all AEs, including SAEs, intensity, relationship to IMP, and deaths will be presented by treatment. Incidence of AEs will be summarized by SOC and PT by treatment. Separate tables will be provided, if relevant, for serious AEs (SAEs) or events leading to withdrawal from study. Separate tables will be provided with summaries per titration period as well (up-titration, stable dosing and down-titration).

#### 9.1.2 *Physical examination*

Clinically significant and non-clinically significant abnormal findings will be specified and presented by patient and summarized by treatment.

#### 9.1.3 *Vital signs*

Vital signs (systolic/diastolic blood pressure, orthostatic blood pressure, pulse, respiratory rate and body temperature) will be summarized by treatment. Data will be presented with absolute and percent change from baseline.

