**Safety assessments**

Safety/tolerability assessments will include: medical history (screening), physical examination (screening and follow-up), 12-lead ECG (all clinic visits), vital signs (all clinic visits), AEs (from baseline visit through follow up visit), assessment of suicidal ideation/behavior (C-SSRS; all clinic visits), and clinical labs (hematology, blood chemistry, and urinalysis; all clinic visits).

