somnolence, malaise, headache, and nausea, consistent with the PK profile of NLX-112. In the Phase 2 study in diabetic neuropathy (DNP) patients, dizziness, headache, nausea, and insomnia were the most common TEAEs. These TEAEs occurred mostly during the up-titration period (when employed) or during the first few days of fixed dose administration and were most frequent at the highest doses. Somnolence was seldom seen in the Phase II studies, perhaps due to the up-titration periods employed in these studies.

Undesirable hemodynamic effects, (i.e., decrease in blood pressure, postural hypotension) were observed in healthy elderly volunteers. Of the twelve elderly subjects, 2 experienced orthostatic hypotension (one episode of moderate intensity in one subject, and 2 episodes of severe orthostatic hypotension with syncope in another subject).

The only SAE noted in the Phase 1 program was one that occurred in a subject that received midazolam as a probe (2 mg oral dose) co-administered with NLX-112 (2.25 mg single oral dose). The SAE, which was interpreted as a 'partial serotonin syndrome' occurred 30 minutes post-dosing and resolved spontaneously within 40 minutes. It should be noted that the subject had previously suffered from nausea, headache, and vomiting on Day -1 (prior to inclusion in the study) and the administration of a benzodiazepine (alprazolam and/or bromazepam) in several subjects exposed to NLX-112 in another Phase 1 study did not induce any serotonergic manifestations.

Two Phase 2 studies provide the bulk of the safety information for NLX-112. A 12-week randomized, placebo-controlled study in 124 DNP patients was well-tolerated and safe at 1 mg BID (i.e. 2 mg/day); the incidence of SAEs was low (3%) and no SAE was related to NLX-112 intake. Only one NLX-112-treated subject withdrew from the study due to a TEAE, a recurrent mild dizziness. Ninety-four percent of TEAEs were mild or moderate. Only dizziness and headache had a greater incidence in the NLX-112 group as compared to placebo (difference > 5%). The most frequently reported TEAEs mainly occurred at the beginning of the treatment and resolved quickly. No clinically significant changes were observed in electrocardiogram (ECG) and laboratory safety tests included glycaemia parameters.

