Study day	Protocol Section	Day -28 to Day -5	Day 1	Day 7 ±1 day	Day 14 ±2 days	Day 21 ±2 days	Day 28 ±2 days	Day 42 ±2 days	Day 49 ±2 days	Day 70 ±7 days
Diary data collection 	11.3.3		X				X	X		
Wearable device data collection 	11.3.6		X				X	X		
L-DOPA challenge	11.3.1		X				X	X		
UDysRS	11.3.2		X				X	X		
Video taping (UDysRS)	11.3.2		X				X	X		
CGI-S/CGI-C 	11.3.5		X				X	X		
KPPS	11.4.1		X				X	X		
PDQ39	11.4.2		X				X	X		
HADS	11.4.3		X				X	X		
ICIQ-OAB	11.4.4		X				X	X		
ESS	11.4.5		X				X	X		
NLX-112 plasma concentration sampling	11.4.6				X	X	X	X		X
Drug accountability	10.5						X	X		X
Baseline symptoms	11.1.10	X								
Adverse events 	11.2.1						X			
Prior and concomitant medications	11.1.6						X			

CGI-S/CGI-C=Clinical Global Impression of Severity and Clinical Global Impression of Change, C-SSRS=Columbia Suicide Severity Rating Scale, ESS=the Epworth Sleepiness Scale, HADS=the Hospital Anxiety Depression Scale, ICIQ-OAB=the International Consultation on Incontinence Questionnaire Overactive Bladder Module,

KPPS=the King's Parkinson's disease Pain Scale, UPDRS=the Unified Parkinson's Disease Rating Scale, MMSE=Mini Mental Status Exam, PDQ39=the Parkinson's disease Quality of Life Scale (39-item), UDysRS=the Unified Dyskinesia Rating Scale

1. Also early withdrawal follow-up visit
2. Confirmation of eligibility
3. Blood pressure (including orthostatic hypotension assessment), pulse, respiratory rate and temperature. At screening and baseline (Visit 1 and Visit 2), vital signs to assess orthostatic hypotension will be conducted in triplicate, 15-20 minutes apart, with the average of the 3 assessments used for exclusion.
4. Body weight at Visit 1 and Visit 9. Height at Visit 1 only.
5. The Modified Hoehn and Yahr scale will be used to establish the PD stage of the patient.
6. Women of child-bearing potential only.
7. Hematology, coagulation, serum biochemistry and urinalysis.
8. C-SSRS: the baseline scale will be used at the first assessment (screening, Visit 1) and the follow-up scale will be used at all subsequent visits.
9. UPDRS - Screening: part IV only. Other visits: parts I-IV
10. PD Home Dyskinesia Diary: 2 consecutive 24-hour diaries taken prior to the visits indicated above.
11. Wearable data collection will take place during a 2-day period prior to the visits indicated above.
12. CGI-S at baseline (Day 1, Visit 2), CGI-C at other visits.

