#### *11.2.3 Vital signs*

Blood pressure (systolic and diastolic) and pulse will be measured in sitting position after at least 5 minutes of rest and then again 3 minutes after standing upright to determine whether the patient has orthostatic hypotension (decrease in systolic blood pressure of at least 20 mm Hg or diastolic blood pressure of at least 10 mm Hg within 2 minutes of the patient standing up, compared to the blood pressure obtained while in the sitting position). At screening and baseline (Visit 1 and Visit 2), the investigator should collect 3 assessments, each taken 15 to 20 minutes apart, in order to obtain an average value. All measurements and the calculated average value should be recorded in the eCRF. At other visits, one assessment is sufficient.

Respiratory rate will be assessed by routine methods. Body temperature will be measured orally using a digital thermometer.

Any vital signs outside the normal ranges at each site will be judged as NCS or CS. The assessment will be recorded in the eCRF. Post-dose vital signs judged as “abnormal, clinically significant” by the Investigator will be reported as AEs.

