**Table VS 1 Vital signs measurements (Full analysis set)**

Assessment (unit)	Result category	Assessment timepoint		NLX-112 (N=XX)	Placebo (N=XX)	Total (N=XX)
[PARAMETER 1]	Measured value (unit)	[Assessment timepoint 1]	n	xx	xx	xx
			Mean (SD)	x.xx (x.xx)	x.xx (x.xx)	x.xx (x.xx)
			Median (Min, Max)	x.xx (x.x, x.x)	x.xx (x.x, x.x)	x.xx (x.x, x.x)
		[Assessment timepoint 2]	n	xx	xx	xx
			Mean (SD)	x.xx (x.xx)	x.xx (x.xx)	x.xx (x.xx)
			Median (Min, Max)	x.xx (x.x, x.x)	x.xx (x.x, x.x)	x.xx (x.x, x.x)
	Absolute change from baseline	[Assessment timepoint 2]	n	xx	xx	xx
			Mean (SD)	x.xx (x.xx)	x.xx (x.xx)	x.xx (x.xx)
			Median (Min, Max)	x.xx (x.x, x.x)	x.xx (x.x, x.x)	x.xx (x.x, x.x)
	Relative change from baseline (%)	[Assessment timepoint 2]	n	xx	xx	xx
			Mean (SD)	x.xx (x.xx)	x.xx (x.xx)	x.xx (x.xx)
			Median (Min, Max)	x.xx (x.x, x.x)	x.xx (x.x, x.x)	x.xx (x.x, x.x)

Data based on the Full analysis set. n: Number of observations. SD: Standard deviation. NC: Not calculated - number of evaluable observations less than 3. NA: Not available - no evaluable observations. SAS program: [PROGRAM NAME].sas. Run by: [USERNAME] YYYY-MM-DDTHH:MM:SS. Data extracted at: YYYY-MM-DDTHH:MM:SS

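### On-treatment falls in standing blood pressure that meet the protocol's definition of orthostatic hypotension, but are not judged clinically significant, are counted in no SAP table

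*SAP*

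**What the plan says.** **Measurement.** Footnote 3 to the schedule of events (Protocol Table 8.1-1) describes vital signs as "Blood pressure (including orthostatic hypotension assessment), pulse, respiratory rate and temperature". The schedule marks them at Visits 1, 2, 4, 5, 6, 7 and 9. Protocol 11.2.3 takes pressure sitting and "then again 3 minutes after standing upright to determine whether the patient has orthostatic hypotension". The limits are a fall of at least 20 mm Hg systolic or "diastolic blood pressure of at least 10 mm Hg within 2 minutes of the patient standing up". Exclusion criterion 3 (Protocol 9.5) uses the same limits but allows 3 minutes. Three assessments are averaged at Visits 1 and 2; one suffices at later visits.

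**Route to an adverse event.** Protocol 11.2.3 states: "Any vital signs outside the normal ranges at each site will be judged as NCS or CS". The judgement goes into the eCRF, and a post-dose value judged abnormal and clinically significant (CS) is reported as an AE.

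**Analysis.** SAP 9.1.3 reads: "Vital signs (systolic/diastolic blood pressure, orthostatic blood pressure, pulse, respiratory rate and body temperature) will be summarized by treatment". Table VS 1 shows n, mean (SD) and median (min, max) of the measured value, of the absolute change and of the "Relative change from baseline". Protocol 17.5.3 has the same content. Neither document says whether orthostatic blood pressure is the standing value or the fall.

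**Known risk.** Protocol 6.1.3 reports: "Of the twelve elderly subjects, 2 experienced orthostatic hypotension", one of them with syncope. Protocol 6.3.1 lists postural hypotension as a potential risk.

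**The concern.** The primary objective is safety and tolerability against placebo, in patients up to 85 years old. One primary endpoint is clinically significant change from baseline in vital signs, which is a categorical outcome. The standing reading exists to answer a yes/no question, yet the planned table answers a different one, about averages.

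The SAP gives ECG an interpretation table (EG 2) and physical examination a categorical table (PE 1). Vital signs have neither, although the not clinically significant/clinically significant (NCS/CS) judgement is recorded. At stake is whether the report's tables can show how many patients per arm met the protocol's own definition while on treatment.

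**Working it through.** The documents give no figure to reproduce here. The check is whether any planned output would show a case, and what a count would be worth.

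**1. Trace a fall through the plan.**

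| On-treatment fall meeting the 20/10 limits | AE tables | Table VS 1 | Listing 16.2.9-1 |
|---|---|---|---|
| Judged CS, with or without symptoms | Counted | Not as a case | Readings listed |
| Judged NCS, not otherwise recorded as an AE | Not counted | Not as a case | Readings listed |
| Never judged (both readings within site range), not otherwise recorded as an AE | Not counted | Not as a case | Readings listed |

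An assumed example of the third row is 138/84 sitting and 114/72 standing. The fall is 138 − 114 = 24 systolic and 84 − 72 = 12 diastolic, so both limits are met. Whether either reading is outside range depends on site ranges that the documents do not give.

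**2. Can Table VS 1 stand in for a count?** Take 16 NLX-112 patients (SAP 4.3) and assumed falls in mm Hg:

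- Sixteen falls of 5: mean 80/16 = 5.0, with 0 cases.
- Three falls of 25 and thirteen of 5/13 (about 0.4): mean (75 + 5)/16 = 5.0, with 3 cases.
- Three falls of 25 and thirteen of 0: mean 75/16 = 4.7, median 0, with 3 cases.

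The same mean therefore fits none or three. Minimum and maximum show one extreme per visit, and only if the variable is the fall. If it is the standing value, a reader can subtract arm means but cannot recover cases.

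**3. Percent change.** If the variable is the difference d, percent change is 100 × (d_visit − d_baseline)/d_baseline. It is undefined when d_baseline = 0, and its sign reverses according to whether the baseline difference is a rise or a fall.

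**4. What a count could show.** With 16 patients and an assumed rate p of meeting the definition on NLX-112, the expected number is 16p and P(at least one) = 1 − (1 − p)^16:

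| p (assumed) | Expected | P(at least one) |
|---|---|---|
| 5% | 0.8 | 0.56 |
| 10% | 1.6 | 0.81 |
| 25% | 4.0 | 0.99 |

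These are rates of meeting the definition, not of going uncounted. Precision is low. Zero of 16 has an exact 95% upper limit of 20.6%; 3 of 16 has an interval of 4.0% to 45.6%; 3/16 against 0/8 gives Fisher p = 0.53.

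**5. Background rates in the protocol.** The elderly volunteers give 2/12 = 16.7% (exact 95% CI 2.1% to 48.4%). Protocol Table 6.1-1 gives drug-related hypotension in 3/113, 2/114 and 2/117 NLX-112 patients. Together that is 7/344 = 2.0%, against 0/112 on placebo. Neither figure measures falls that escape the AE tables.

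**The case against.** A reader might infer that asymptomatic cases never reach the safety tables, or that only patients reporting symptoms would appear. Protocol 11.2.3 contradicts this. A value judged clinically significant is an AE without any symptom requirement, the AE definition includes unfavourable signs, and investigators may record what they observe. An investigator could also treat a fall meeting the definition as abnormal even with both readings in range, since definition and judgement rule stand in the same section.

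A reader might also infer that the report could not state the number of cases. The readings are listed by patient. About 24 patients with five post-baseline clinic visits give at most 24 × 5 = 120 sitting/standing pairs, which can be counted by hand. What is missing is a planned, prespecified count, not the data.

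A third tempting step is to apply 2/12 to 16 patients and expect about 2.7 missed cases. Those two volunteers had events graded moderate and severe, the kind the AE tables would capture. Protocol 6.1.3 gives neither dose nor titration for them. This trial excludes orthostatic hypotension at entry and up-titrates over 4 weeks. The lower figure from Table 6.1-1 is not specifically orthostatic and comes from another population.

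All three objections stand as limits on the point. None supplies the missing count.

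**Conclusion.** The gap is real and modest. The plan schedules a yes/no determination of a named risk at every clinic visit and then provides no output for it. Falls meeting the limits but judged NCS, or never judged, are counted in no table unless recorded as an AE by another route. The variable that is summarised is undefined, and its percent change is unsuitable if it is the difference.

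The number of uncounted cases is unknown, and the documents cannot bound it. It depends on site ranges and investigator judgement, neither of which they describe. With 16 and 8 patients, the added count would describe the arms and would not test them. The conclusion rests on the text of SAP 9.1.3, the table shells and Protocol 11.2.3. The numerical examples only illustrate why averages cannot replace a count.

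**What to change.** - In SAP 9.1.3, define orthostatic blood pressure as standing minus sitting pressure, systolic and diastolic separately. Show absolute change only for this variable.
- Add to Table VS 1 the n (%) of patients per arm meeting the protocol's mm Hg limits at each visit and at any on-treatment visit (Visits 4 to 7 as scheduled).
- Show the scheduled Visit 9 separately. Visit 9 is also the early-withdrawal visit, so identify those assessments; otherwise a patient who leaves before Visit 4 drops out of the on-treatment count.
- Add an NCS/CS table for vital signs on the model of Table EG 2.
- Before the flag is programmed, reconcile the 2-minute wording in Protocol 11.2.3 with the 3-minute wordings there and in exclusion criterion 3.

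The cost is SAP wording and a small block of output from data already collected, with no new assessment. The downside is noise. Baseline averages three assessments and later visits use one. If errors are independent, a single assessment has √3 = 1.7 times the error SD of the average, and a patient has four chances to cross the limit on treatment. Some cases will be spurious, so label the counts descriptive and read them against the placebo arm.

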#### 9.1.4 *12-lead ECG*

All ECGs will be categorized as "normal", "abnormal, not clinically significant", or "abnormal, clinically significant" (as judged by the Investigator) and summarized by treatment using frequency tables.

#### 9.1.5 *Columbia Suicide Severity Rating Scale (C-SSRS)*

C-SSRS data will be listed by treatment, patient and visit and summarized by treatment.

#### 9.1.6 *Safety laboratory analyses*

Safety laboratory data will be summarized by treatment with absolute and percent change from baseline at each visit.

### 9.2 Analysis of secondary endpoints

#### 9.2.1 *Statistical inferential analysis of efficacy endpoints*

Absolute change from baseline in efficacy endpoints (secondary and exploratory endpoints) will generally be analysed using a linear mixed model with treatment, visit and the interaction

treatment\*visit as fixed categorical effects and subject within treatment as a random effect. The baseline value of the dependent variable will be included in the model as a continuous covariate, to account for possible differences in change from baseline outcomes due the starting baseline level. Visit will be modelled as a repeated effect. Kenward-Roger's approximation for degrees of freedom will be used.

Providing a significant type III F-test for the interaction effect treatment\*visit, differences between least square estimates of NLX-112 and placebo for the same visit (i.e. from the interaction term treatment\*visit, where visit is the same for both NLX-112 and placebo) will be estimated and the corresponding p-value will be presented in tables. In addition, differences between least square estimates of each post-baseline visit and baseline for NLX -112 and placebo respectively (i.e. from the interaction term treatment\*visit, where treatment is the same for the post-baseline and the baseline visit) will be estimated and the corresponding p-value will be presented in tables.

The model proposed above will be used for FAS and is valid, as long as the underlying data is missing at random (MAR). As a sensitivity analysis, the model will also be run for PPS, serving as a validity check for the main FAS analysis. The sensitivity analysis will be a complete case analysis, i.e., only patients with no missing data for the dependent variable will be used.

Model diagnostics, for example Shapiro-Wilk's test for a normally distributed residual term and Leven's test for the homoscedasticity assumption of the residual term as well as Q-Q plots and plotting residuals vs. predicted values, will be performed. If model assumptions are deemed to be violated, an attempt will be made to transform the dependent variable in order to fulfil model diagnostics.

A box-cox model will be used to find the most appropriate transformation of data. Lambda values between -3 and 3 will be tested using increments of 0.25. The dependent variable will be transformed accordingly, and the linear mixed model rerun on transformed data. Subsequently, the same model diagnostics as described above will be performed. If model assumptions are deemed to be violated, the linear mixed model approach will not be further pursued for the corresponding dependent variable.

If transforming data according to the above method fails, the analysis will be done using non-parametric methods. A Wilcoxon rank sum test will be used to assess statistically significant differences between active treatment and placebo for relative change from baseline in efficacy endpoints for all post-baseline visits respectively. Furthermore, a Wilcoxon signed rank test will be performed for each post-baseline visit and baseline for NLX -112 and placebo respectively to assess statistically significant differences between each post-baseline visit and baseline for each treatment separately.

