## 9.9 Randomization

On Day 1, patients will be randomized to receive either NLX-112 or placebo. The randomization will be performed per site using SAS with the ratio 2:1 for active treatment to placebo. This will give approximately 16 patients receiving NLX-112 and 8 patients receiving

placebo in total in the study. In addition, approximately the same ratio will be attained within each site. The study will use competitive enrollment between sites.

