#### **11.3.5 *Clinical Global Impression of Severity and Change (CGI-S, CGI-C)***

The CGI-C is a clinician-oriented scale that assesses the total improvement in the patient's condition relative to the clinical global impression of severity (CGI-S) scale conducted at baseline. The CGI-C rates the patient's condition from 0 to 7, with a rating of 0 indicating "no assessment", a rating of 1 indicating "very much better", and a rating of 7 indicating "very much worse".

For timing of assessments, refer to Table 8.1-1.

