#### 4.3 Randomization and number of subjects

On Day 1, patients were randomized to receive either NLX-112 or placebo with the ratio 2:1 for active treatment to placebo. This will give approximately 16 patients who received NLX-112 and 8 patients who received placebo in the study. In addition, approximately the same ratio was intended to be attained within each site. The study used competitive enrolment between 5 sites.

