#### **9.2.5 Clinical Global Impression of Change (CGI-C) in overall PD symptoms**

Change from baseline in CGI-C in overall PD symptoms to Visit 6 (Day 28) and Visit 7 (Day 42) respectively will be summarized using descriptive statistics. In this analysis, rating 0, indicating “no assessment” will be excluded. CGI-C will be analysed using inferential statistics as described under 9.2.1 above.

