**Table CG 1 CGI-S and CGI-C in overall PD symptoms (Full analysis set)**

Assessment	Assessment timepoint		NLX-112 (N=XX)	Placebo (N=XX)	Total (N=XX)
CGI-S	[Assessment timepoint 1]	n	xx	xx	xx
		Mean (SD)	x.xx (x.xx)	x.xx (x.xx)	x.xx (x.xx)
		Median (Min, Max)	x.xx (x.x, x.x)	x.xx (x.x, x.x)	x.xx (x.x, x.x)
CGI-C	[Assessment timepoint 2]	n	xx	xx	xx
		Mean (SD)	x.xx (x.xx)	x.xx (x.xx)	x.xx (x.xx)
		Median (Min, Max)	x.xx (x.x, x.x)	x.xx (x.x, x.x)	x.xx (x.x, x.x)
CGI-C	[Assessment timepoint 3]	LMM a p-value	xxxxx b	xxxxx c	xxxxx d
		n	xx	xx	xx
		Mean (SD)	x.xx (x.xx)	x.xx (x.xx)	x.xx (x.xx)
		Median (Min, Max)	x.xx (x.x, x.x)	x.xx (x.x, x.x)	x.xx (x.x, x.x)
		LMM a p-value	xxxxx b	xxxxx c	xxxxx d

Data based on the Full analysis set. SAS program: [PROGRAM NAME].sas. Run by: [USERNAME] YYYY-MM-DDTHH:MM:SS. Data extracted at: YYYY-MM-DDTHH:MM:SS

Specify CGI-S or CGI-C in the assessment column. Do not include rating 0, indicating “no assessment” in the summary/analysis. There is no result category column, since change from baseline is included in the definition of CGI-C. Produce the table above for PPS as well, providing there is any de facto difference between the analysis sets. If the LMM is performed using transformed data, insert a footnote about this as well. If the LMM approach is dropped in favour of non-parametric tests, update the table and footnotes accordingly.

*10.2.3.5 Dyskinesia scores measured by a wearable dyskinesia assessment device*

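### Randomisation is 2:1 within site but the SAP 9.2.1 model has no site term; if sites differ in rated change, the CGI-C between-arm test is mildly conservative and the within-arm tests reject too often (minor)

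*SAP*

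**What the plan says.** Protocol 9.9: "The randomization will be performed per site using SAS with the ratio 2:1 for active treatment to placebo". It expects roughly that ratio inside each site, but names no block size. SAP 4.3 repeats that "approximately the same ratio was intended to be attained within each site", with 5 sites enrolling competitively and about 16 and 8 patients per arm.

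SAP 9.2.1 models change from baseline with treatment, visit and treatment by visit "as fixed categorical effects and subject within treatment as a random effect", and adds the baseline value as a covariate. The footnote to Table UD 1 lists the same terms. Site is in neither list, nor in SAP Table 2 (changes from the protocol). The only methods remark on site, at the start of SAP 9, says that small numbers are why there are no by-site summaries and that listings will show site.

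For the clinician's global rating, SAP 9.2.5 states: "CGI-C will be analysed using inferential statistics as described under 9.2.1 above". Protocol 11.3.5 explains: "The CGI-C is a clinician-oriented scale that assesses the total improvement" relative to the baseline severity rating. The note to Table CG 1 says: "There is no result category column, since change from baseline is included in the definition of CGI-C". That table has p-value cells for each arm separately as well as for the comparison of arms.

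Per-visit comparisons depend on a prior test: "Providing a significant type III F-test for the interaction effect" of treatment by visit.

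**The concern.** Allocating 2:1 inside each site largely removes differences between sites from the true error of the treatment comparison. A model without site still counts those differences as residual variance. The standard error of the arm difference is then too large and the test too cautious.

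CGI-C is where this can matter. Raters work locally (Protocol 11.3), and a lenient or strict rater shifts every CGI-C score at that site, with no same-scale baseline to cancel the shift. For UDysRS Parts III/IV and UPDRS Part III a constant rater offset largely drops out of the change score, and for UDysRS there are backup video recordings (Protocol 11.3.2). The diary, the wearable device and the patient-completed scales do not depend on a site rater.

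Within one arm nothing balances the site differences. Patients from the same site are correlated, the model treats them as independent, and the standard error of the arm mean is too small. The stake is some lost power in one comparison and too many false positives in another, both for a secondary endpoint.

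**Working it through.** There is no sample size or power figure in the plan to reproduce. The split is consistent: 24 × 2/3 = 16, 24 × 1/3 = 8, and 5 sites of 4 to 6 patients give 20 to 30.

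**Inputs.** From the documents: 24 patients, 5 sites, 2:1 per site, two-sided 5%, ratings 1-7, visits on Days 28 and 42. Assumed: within-site SD 1 point, and site leniency SD s = 0.33, 0.5 or 0.65 points. The site share of variance is s²/(1 + s²): 0.109/1.109 = 10%, 0.25/1.25 = 20%, 0.4225/1.4225 = 30%.

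**Between arms, one visit, exact balance.** The true variance of the arm difference is 1 × (1/16 + 1/8), because site cancels. With equal spread over 5 sites, the pooled within-arm variance that ignores site has expectation 1 + k·s², where k = [(16 − 16/5) + (8 − 8/5)]/22 = 19.2/22 = 0.873. The test therefore uses an effective critical value of 2.074 × √(1 + 0.873·s²) on 22 df.

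| Site share | Effective critical value | Approximate level |
|---|---|---|
| 10% | 2.074 × √1.095 = 2.170 | 4.1% |
| 20% | 2.074 × √1.218 = 2.289 | 3.2% |
| 30% | 2.074 × √1.369 = 2.426 | 2.4% |

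Real sites are not multiples of 3, so balance is imperfect and the effect is weaker. Simulation with the rating rounded to 1-7, blocks of 3, and sites of 5/5/5/5/4 or 8/6/5/3/2 gives about 4.0-4.6, 3.5-3.9 and 3.0-3.6%. On an unrounded scale the figures are slightly lower (3.8-4.2, 3.1-3.8 and 2.9-3.0%). With unblocked 2:1 allocation within site the level at 20-30% is 4.6-5.2%, so there is no conservatism.

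**Within the NLX-112 arm.** The true variance of the arm mean is 1/16 + s²/5. The variance used is (1 + 0.853·s²)/16, where 0.853 = (16 − 3.2)/15. The critical value on 15 df is 2.131, divided by the square root of true over used.

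| Site share | True / used variance | Effective critical value | Approximate level |
|---|---|---|---|
| 10% | 0.0843 / 0.0683 | 1.919 | 7.4% |
| 20% | 0.1125 / 0.0758 | 1.750 | 10.1% |
| 30% | 0.1470 / 0.0850 | 1.621 | 12.6% |

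Simulation gives about 7-9, 10-12 and 12-15%. This takes a rating of 4 as no change, which the SAP does not define, and treats the test as ungated.

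**What adding site would return.** A site shift that is the same at both visits cancels in the treatment by visit contrast, so the gate is unaffected. For an assumed effect of 1 point on Day 42, 4,000 simulated trials per setting gave:

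- Same effect on Day 28: the gate passes in 5-6% of trials; gain 0-0.4 points.
- Half the effect on Day 28: the gate passes in 24-25%; gain 0.6-0.7 points at a 10% share and 1.2-1.4 at 20%.
- Effect on Day 42 only: the gate passes in 70%; gain about 5 points at a 20% share.

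**What the random term costs.** Its simulated level is 4.9-6.1% over shares of 0-30% (Monte Carlo standard error 0.35). The site variance is estimated as zero in 56-59% of trials when sites do not differ and in 20-26% at a 20% share. Held to a true 5% level, it costs 0-1 point of power when sites do not differ.

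**The case against.** The case for leaving the model alone is reasonable. There are 24 patients and 1 or 2 placebo patients per site, CGI-C is one of eight secondary endpoints, and SAP 5.8 calls the tests exploratory. Small numbers may well be the unstated reason. That supports a low priority, but SAP 9 applies the small-sample remark to summaries only, not to the model.

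All the benefit rests on an assumed site variance, and blocking is inferred from the within-site ratio that Protocol 9.9 expects. Both points stand as conditions. Site is also only a proxy for rater, since Protocol 11.3 asks for the same rater at each visit only where possible and does not fix one rater per site. Two raters per site with independent leniency weaken the effect: the level without site is then 4.0-4.1% at a leniency SD of 0.5.

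A reader might infer that adding site recovers several points of power on the planned analysis. That holds only for an ungated per-visit test, which SAP 9.2.1 does not plan. An effect absent on Day 28 would be needed under the gate, although the Protocol 8.1 schedule has reached 1.75 of 2 mg/day by then.

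A reader might also infer that the non-parametric fallback should be made site-aligned. That fallback tests "differences between active treatment and placebo for relative change from baseline in efficacy endpoints for all post-baseline visits respectively". CGI-C has no baseline on its own scale, so the SAP defines no such test for it, and there is nothing to align until it does.

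**Conclusion.** The omission is real and minor. If sites differ in rated change and allocation is blocked within site, the CGI-C comparison of NLX-112 with placebo runs at about 3.0-4.6% instead of 5% over assumed site shares of 10-30%. If allocation is not blocked it stays near 5%, and if sites do not differ nothing is lost.

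Two stronger readings fail. The missing term does not inflate false positives between arms. Nor can one say that the error is always on the safe side, because the planned within-arm CGI-C tests run at about 7-15% over the same range. Those within-arm figures depend on an assumed no-change value. They also apply to the test on its own; SAP 9.2.1 does not make clear whether the interaction gate covers it.

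The interaction gate limits the between-arm comparison far more than the missing site term does.

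**What to change.** Add site as a random intercept to the SAP 9.2.1 model for CGI-C. Run a site-adjusted sensitivity analysis for UDysRS Parts III/IV and UPDRS Part III. State what value the within-arm CGI-C tests compare against. By-site summaries can stay omitted.

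This takes one model term and a few sentences. No new data are needed, because site is already recorded. The SAP should say what happens when the site variance is estimated as zero, which will be common with 5 sites, and should accept a level of up to about 6% and a loss of 0-1 point of power if sites do not differ. A random intercept also carries site variance into the standard error of each arm mean, which is the right direction for the within-arm tests. How fully it corrects them with 5 sites was not simulated, so those p-values should still be read cautiously.
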